APPENDIX 2. CLINICAL LABORATORY ASSESSMENTS AND REVIEW AND ASSESSMENT OF POTENTIAL HY'S LAW CASES

- The tests detailed in [Table A2-1](#) will be performed by the local laboratory.
- Protocol specific- requirements for inclusion or exclusion of subjects are detailed in [Section 5.1](#) and [Section 5.2](#) of the protocol, respectively.
- Additional tests may be performed at any time during the study as determined necessary by the investigator or required by local regulations.
- Pregnancy Testing: Refer to [Section 5.1](#) for screening criteria, to [Appendix 4](#) for women of childbearing potential (WOCBP) criteria, and to the Schedule of Activities (SoA; [Table 1](#)) for timepoints.
- The results of each test must be entered into the electronic Case Report Form (eCRF).
- Investigators must document their review of each laboratory safety report.

Table A2-1 Protocol-Required Safety Laboratory Assessments

Laboratory Assessments	Parameters							
Hematology	RBC Count	RBC Indices: MCV, MCH, % Reticulocytes						
	Hemoglobin	WBC count with Differential: Neutrophils, Lymphocytes, Monocytes, Eosinophils, Basophils, Bands (if available)						
	Hematocrit							
	Platelet count							
Clinical Chemistry ¹	Sodium	Potassium	Chloride	Bicarbonate/Carbon Dioxide				
	Blood urea nitrogen	Creatinine	Glucose (non-fasting)	Total Protein				
	Albumin	Phosphorus	Calcium	Magnesium				
	Uric Acid	ALT/AST	Total and direct bilirubin	ALP				
	Gamma-glutamyl transferase	Lipase						
CPK isoenzymes ²	Total and skeletal muscle (MM) component (not required for screening purposes)							
Coagulation Tests	Prothrombin time/INR, aPTT or PTT							
Routine Urinalysis	Appearance, specific gravity, pH, glucose, protein/albumin, blood, ketones, bilirubin, urobilinogen, nitrites, leukocyte esterase							
	Microscopic examination (if blood or protein is abnormal)							

Table A2-1 Protocol-Required Safety Laboratory Assessments

Laboratory Assessments	Parameters
Other Screening Tests	Follicle stimulating hormone and estradiol (as needed in women of nonchildbearing potential only) ³ Highly sensitive blood or urine hCG pregnancy test (as needed for women of childbearing potential) ⁴ Serology ⁵ : HBsAg, HBcAb, and hepatitis C virus antibody. Additional testing (eg, hepatitis B viral load, HBsAb, hepatitis B core IgM antibody) may be required if results are inconclusive or positive for surface antigen/core antibody.

Abbreviations: ALP = alkaline phosphatase; ALT = alanine aminotransferase; aPTT = activated partial thromboplastin time; AST = aspartate aminotransferase; CPK = creatine phosphokinase; hCG = human chorionic gonadotropin; HBcAb = hepatitis B virus core antibody; HBsAg, hepatitis B virus surface antigen; IEC = Independent Ethics Committee; IRB, Institutional Review Board; INR, international normalized ratio; MCH = mean corpuscular hemoglobin; MCV = mean corpuscular volume; PTT = partial thromboplastin time; RBC = red blood cell; SAE = serious adverse event; ULN = upper limit of normal; WBC = white blood cell.

¹ Concurrent elevation of AST or ALT $>3 \times$ ULN AND total bilirubin $>2 \times$ ULN or INR >1.5 in the absence of cholestasis and other causes (eg, viral hepatitis, other pre-existing or acute liver disease, or another drug capable of the observed injury), which may indicate severe drug-induced liver injury (possible Hy's law case). All events with the defined biochemical abnormalities must be reported as an SAE; and study medications should be permanently discontinued.

² Variations of CPK isoenzymes are acceptable (CK, CKMB, Troponin I)

³ See [Appendix 4](#).

⁴ Local urine testing will be standard for the protocol unless blood testing is required by local regulation or IRB/IEC. For screening, a blood test is required.

⁵ For Serology:

- Negative HBsAg test is required at screening
- Negative total hepatitis B core antibody (HBcAb) test at screening, or positive total HBcAb test followed by a negative hepatitis B virus (HBV) DNA test at screening. (The HBV DNA test must be performed for subjects who have a negative HBsAg test and a positive total HBcAb test.)
- Negative hepatitis C virus (HCV) antibody test at screening, or positive HCV antibody test followed by a negative HCV RNA test at screening.

Review and Assessment of Potential Hy's Law Cases

The investigator is responsible for determining whether a subject meets potential Hy's Law criteria at any point during the study. All sources of hepatic biochemistry laboratory data available to the investigator should be reviewed to identify potential Hy's Law events; this includes samples taken at scheduled study visits and other visits, including central and all local laboratory evaluations, even if collected outside of the study visits.

The following are the key components used to detect potential Hy's Law cases:

- Hepatocellular injury, indicated by 3-fold or greater elevations above the upper limit of normal (ULN) of alanine aminotransferase (ALT) or aspartate aminotransferase (AST)
- Elevation of serum total bilirubin to $>2 \times$ ULN (suggesting hepatic functional compromise), without initial findings of cholestasis (elevated serum alkaline phosphatase [ALP])
- No other reason can be found to explain the combination of increased aminotransferase(s) and total bilirubin, such as viral hepatitis A, B, or C; preexisting or acute liver disease; or another drug capable of causing the observed injury

Any potential Hy's Law case (as described above) should be handled as a serious adverse event (see reporting requirements in [Appendix 3](#)) associated with the use of the drug and reported to the Sponsor promptly (ie, even before all other possible causes of liver injury have been

excluded). It should be promptly reported to the Sponsor before fully working up the subject to rule out other etiologies. The case should be reported with the seriousness criterion of medically significant selected, and should include all available information, especially that needed for evaluating the severity and likelihood that the drug caused the reaction and should initiate a close follow-up until complete resolution of the problem and completion of all attempts to obtain supplementary data.

APPENDIX 3. ADVERSE EVENTS: DEFINITIONS AND PROCEDURES FOR RECORDING, EVALUATING, FOLLOW-UP, AND REPORTING

Definition of Adverse Event (AE)

AE Definition

• An adverse event (AE) is any untoward medical occurrence in a subject or clinical study subject, temporally associated with the use of study treatment, whether or not considered related to the study treatment.• NOTE: An AE can therefore be any unfavorable and unintended sign (including an abnormal laboratory finding), symptom, or disease (new or exacerbated) temporally associated with the use of study treatment.

Events Meeting the AE Definition

• Any abnormal laboratory test results (hematology, clinical chemistry, or urinalysis) or other safety assessments (eg, electrocardiogram [ECG], radiological scans, vital signs measurements), including those that worsen from baseline, considered clinically significant in the medical and scientific judgment of the investigator (ie, not related to progression of underlying disease or laboratory value changes that require treatment or adjustment to current study therapy).• Exacerbation of a chronic or intermittent preexisting condition including either an increase in frequency and/or intensity of the condition.• New conditions detected or diagnosed after study treatment administration even though it may have been present before the start of the study.• Signs, symptoms, or the clinical sequelae of a suspected drug-drug interaction.• Signs, symptoms, or the clinical sequelae of a suspected overdose of either study treatment or a concomitant medication. Overdose per se will not be reported as an AE/serious adverse event (SAE) unless it is an intentional overdose taken with possible suicidal/self-harming intent. Such overdoses should be reported regardless of sequelae.

Events NOT Meeting the AE Definition

• The disease/disorder being studied or expected progression, signs, or symptoms of the disease/disorder being studied, unless more severe than expected for the subject's condition.• Medical or surgical procedure (eg, endoscopy, appendectomy): the condition that leads to the procedure is the AE.• Situations in which an untoward medical occurrence did not occur (social and/or convenience admission to a hospital).• Anticipated day-to-day fluctuations of preexisting disease(s) or condition(s) present or detected at the start of the study that do not worsen.

Definition of SAE

If an event is not an AE per definition above, then it cannot be an SAE, even if serious conditions are met (eg, hospitalization for signs/symptoms of the disease under study, death due to progression of disease).

A SAE is defined as any untoward medical occurrence that, at any dose:
a. Results in death
b. Is life threatening The term 'life threatening' in the definition of 'serious' refers to an event in which the subject was at risk of death at the time of the event. It does not refer to an event that hypothetically might have caused death if it had been more severe.
c. Requires inpatient hospitalization or prolongation of existing hospitalization In general, hospitalization signifies that the subject has been detained (usually involving at least an overnight stay) at the hospital or emergency ward for observation and/or treatment that would not have been appropriate in the physician's office or outpatient setting. Complications that occur during hospitalization are adverse events (AEs). If a complication prolongs hospitalization or fulfills any other serious criteria, the event is serious. When in doubt as to whether "hospitalization" occurred or was necessary, the AE should be considered serious. Hospitalization for elective treatment of a preexisting condition that did not worsen from baseline is not considered an AE.
d. Results in persistent disability/incapacity 
• The term disability means a substantial disruption of a person's ability to conduct normal life functions.• This definition is not intended to include experiences of relatively minor medical significance, such as uncomplicated headache, nausea, vomiting, diarrhea, influenza, and accidental trauma (eg, sprained ankle), which may interfere with or prevent everyday life functions, but do not constitute a substantial disruption.
e. Is a congenital anomaly/birth defect Abnormal pregnancy outcomes (eg, spontaneous abortion, fetal death, stillbirth, congenital anomalies, ectopic pregnancy) are considered SAEs.
f. Other situations 
• Medical or scientific judgment should be exercised in deciding whether SAE reporting is appropriate in other situations, such as important medical events that may not be immediately life threatening or result in death or hospitalization but may jeopardize the subject or may require medical or surgical intervention to prevent one of the other outcomes listed in the above definition. These events should usually be considered serious. Examples of such events include other invasive or malignant cancers, intensive treatment in an emergency room or at home for allergic bronchospasm, blood dyscrasias or convulsions that do not result in hospitalization, or development of drug dependency or drug abuse. 
Potential Hy's Law cases that meet the description outlined in Appendix 2 should be reported as SAE.

Recording and Follow-up of AE and/or SAE

AE and SAE Recording

When an adverse event (AE)/serious adverse event (SAE) occurs, it is the responsibility of the investigator to review all documentation (eg, hospital progress notes, laboratory reports, and diagnostics reports) related to the event and report pertinent information.The investigator will then record all relevant AE/SAE information in the electronic case report form (eCRF). Additionally, investigative sites should report SAEs within 24 hours of becoming aware of the event using the paper SAE report form. See section below on the reporting of SAEs.It is not acceptable for the investigator to send photocopies of the subject's medical records in lieu of completion of the AE/SAE Case Report Form (CRF) and SAE report form. Only pertinent information should be reported.There may be instances when copies of medical records for certain cases are requested by the Sponsor or designee. In this case, all subject identifiers, with the exception that the subject number will be redacted on the copies of the medical records before submission to the Sponsor or designee.The investigator will attempt to establish a diagnosis of the event based on signs, symptoms, and/or other clinical information. Whenever possible, the diagnosis (not the individual signs/symptoms) will be documented as the AE/SAE.
Assessment of Intensity

The investigator will assess intensity (severity) for each AE and SAE reported during the study using the definitions found in the National Cancer Institute Common Terminology Criteria for Adverse Events Version 5 (NCI CTCAE v5) or later. The NCI CTCAE v5 displays Grades 1 through 5 with unique clinical descriptions of severity for each referenced AE. If a subject experiences any AE not listed in the NCI CTCAE v5, the following grading system should be used to assess severity:
 
Grade 1 (Mild) – experiences which are usually transient, requiring no special treatment, and not interfering with the subject's daily activitiesGrade 2 (Moderate) – experiences which introduce some level of inconvenience or concern to the subject, and that may interfere with daily activities, but are usually ameliorated by simple therapeutic measuresGrade 3 (Severe) – experiences that are unacceptable or intolerable, significantly interrupt the subject's usual daily activity, and require systemic drug therapy or other treatmentGrade 4 (Life threatening) – experiences that cause the subject to be in danger of life-threatening consequences and urgent intervention is requiredGrade 5 (Death) – experiences which result in subject death 
The terms "severe" and "serious" are not synonymous. An AE that is assessed as Grade 3 or 4 should not be confused with an SAE. Severity is a category utilized for rating the intensity of an event; and both AEs and SAEs can be assessed as Grade 3 or 4. An event is defined as serious when it meets at least 1 of the predefined seriousness, as described in the definition of an SAE, not only when it is rated as Grade 3 or 4.

Assessment of Causality

- The investigator is obligated to assess the relationship between both study interventions/study treatment and each occurrence of each AE/SAE.
- A “reasonable possibility” of a relationship conveys that there are facts, evidence, and/or arguments to suggest a causal relationship, rather than a relationship cannot be ruled out.
- The investigator will use clinical judgment to determine the relationship.
- Alternative causes, such as underlying disease(s), concomitant therapy, and other risk factors, as well as the temporal relationship of the event to study treatment administration will be considered and investigated.
- The investigator will also consult the Investigator’s Brochure (IB) and applicable prescribing information in his/her assessment.
- For each AE/SAE, the investigator **must** document in the medical notes that he/she has reviewed the AE/SAE and has provided an assessment of causality.
- There may be situations in which an SAE has occurred, and the investigator has minimal information to include in the initial report to the Sponsor or designee. However, **it is very important that the investigator always makes an assessment of causality for every event before the initial transmission of the SAE data to the Sponsor or designee.**
- The investigator may change his/her opinion of causality in light of follow-up information and send a SAE follow-up report with the updated causality assessment.
- The causality assessment is one of the criteria used when determining regulatory reporting requirements.

Follow-up of AEs and SAEs

- The investigator is obligated to perform or arrange for the conduct of supplemental measurements and/or evaluations as medically indicated or as requested by the Sponsor or designee to elucidate the nature and/or causality of the AE or SAE as fully as possible. This may include additional laboratory tests or investigations, histopathological examinations, or consultation with other health care professionals.
- If a subject dies during participation in the study or during a recognized follow-up period, the investigator will provide the Sponsor or designee with a copy of any postmortem findings including histopathology.
- New or updated information will be recorded in the originally completed eCRF.
- The investigator will submit any updated SAE data within 24 hours of receipt of the information on an updated SAE report form to either the email or fax listed below.

Reporting of SAES**SAE Reporting to the Sponsor or Designee via Paper CRF**

- Investigative sites should report SAEs within 24 hours of becoming aware of the event to the Fortrea Pharmacovigilance department using the paper SAE report form and any supporting documentation either by email or fax.

Email: [contact]
[contact]
- In rare circumstances and in the absence of email or facsimile equipment, notification by telephone to the Medical Monitor is acceptable with a copy of the SAE report form sent to Fortrea when email and fax becomes available.
- Contacts for SAE reporting and the SAE report form can be found in the Regulatory binder.

APPENDIX 4. CONTRACEPTIVE GUIDANCE AND COLLECTION OF PREGNANCY INFORMATION

Definitions

Woman of Childbearing Potential (WOCBP)

A woman is considered fertile following menarche and until becoming postmenopausal, unless permanently sterile (see below).

If fertility is unclear (eg, amenorrhea in adolescents or athletes) and a menstrual cycle cannot be confirmed before first dose of study treatment, additional evaluation should be considered.

Women in the following categories are not considered WOCBP:

1. Premenarchal
2. Premenopausal female with one of the following:
 - Documented hysterectomy
 - Documented bilateral salpingectomy
 - Documented bilateral oophorectomy

For individuals with permanent infertility due to an alternate medical cause other than the above, (eg, mullerian agenesis, androgen insensitivity), investigator discretion should be applied to determining study entry.

Note: Documentation can come from the site personnel's review of the subject's medical records, medical examination, or medical history interview.

3. Postmenopausal female
 - A postmenopausal state is defined as no menses for 12 months without an alternative medical cause.
A high follicle stimulating hormone (FSH) and estradiol level in the postmenopausal range may be used to confirm a postmenopausal state in women not using hormonal contraception or hormonal replacement therapy (HRT). However, in the absence of 12 months of amenorrhea, confirmation with more than one FSH and estradiol measurement is required.
 - Females on HRT and whose menopausal status is in doubt will be required to use one of the non-estrogen hormonal highly effective contraception methods if they wish to continue their HRT during the study. Otherwise, they must discontinue HRT to allow confirmation of postmenopausal status before study enrollment.

Contraception Guidance

CONTRACEPTIVES¹ ALLOWED DURING THE STUDY INCLUDE:	
Highly Effective Methods² That Have Low User Dependency Failure rate of <1% per year when used consistently and correctly.	

 • Implantable progestogen only hormone contraception associated with inhibition of ovulation ³ • Intrauterine device (IUD) • Intrauterine hormone-releasing system (IUS)³ • Bilateral tubal occlusion 	
Vasectomized partner (Vasectomized partner is a highly effective contraceptive method provided that the partner is the sole sexual partner of the woman of childbearing potential (WOCBP) and the absence of sperm has been confirmed. If not, an additional highly effective method of contraception should be used. Spermatogenesis cycle is approximately 90 days.)	
Highly Effective Methods³ That Are User Dependent Failure rate of <1% per year when used consistently and correctly.	
Combined (estrogen- and progestogen-containing) hormonal contraception associated with inhibition of ovulation ³ 
 • oral • intravaginal • transdermal • injectable 	
Progestogen-only hormone contraception associated with inhibition of ovulation ³ 
 • oral • injectable 	
Sexual abstinence (Sexual abstinence is considered a highly effective method only if defined as refraining from heterosexual intercourse during the entire period of risk associated with the study treatment. The reliability of sexual abstinence needs to be evaluated in relation to the duration of the study and the preferred and usual lifestyle of the subject.)	

Note: Periodic abstinence (calendar, symptothermal, post-ovulation methods), withdrawal (coitus interruptus), spermicides only, and lactational amenorrhea method are NOT acceptable methods of contraception. Male condom and female condom should not be used together (due to risk of failure with friction).

¹ Contraceptive use by men or women should be consistent with local regulations regarding the use of contraceptive methods for those participating in clinical studies. Contraceptive requirements do not apply to subjects who are exclusively in same sex relationships.

² Failure rate of <1% per year when used consistently and correctly. Typical use failure rates differ from those when used consistently and correctly.

³ Hormonal contraception efficacy may potentially be decreased due to interaction with sotorasib thus male condoms must be used in addition to hormonal contraception.

COLLECTION OF PREGNANCY INFORMATION

Male Subjects with Partners Who Become Pregnant

- The investigator will attempt to collect pregnancy information on any male subject's female partner who becomes pregnant while the male subject is in this study. This

applies only to male subjects who receive RMC4630 and sotorasib under this protocol.

- After obtaining the necessary signed informed consent from the pregnant female partner directly, the investigator will record pregnancy information on the appropriate form provided in the regulatory binder and submit it to the Sponsor within 24 hours of learning of the partner's pregnancy. The female partner will also be followed to determine the outcome of the pregnancy. Information on the status of the mother and child will be forwarded to the Sponsor. Generally, the follow-up will be no longer than 6 to 8 weeks following the estimated delivery date. Any termination of the pregnancy will be reported regardless of fetal status (presence or absence of anomalies) or indication for the procedure.

Female Subjects Who Become Pregnant

- The investigator will collect pregnancy information on any female subject who becomes pregnant while participating in this study. Information will be recorded on the appropriate form and submitted to the Sponsor within 24 hours of learning of a subject's pregnancy.
- The subject will be followed to determine the outcome of the pregnancy. The investigator will collect follow-up information on the subject and the neonate, and the information will be forwarded to the Sponsor. Generally, follow-up will not be required for longer than 6 to 8 weeks beyond the estimated delivery date. Any termination of pregnancy will be reported, regardless of fetal status (presence or absence of anomalies) or indication for the procedure.
- While pregnancy itself is not considered to be an adverse event (AE) or serious adverse event (SAE), any pregnancy complication or elective termination of a pregnancy will be reported as an AE or SAE. A spontaneous abortion is always considered to be an SAE and will be reported as such. Any poststudy pregnancy related SAE considered reasonably related to the study treatment by the investigator will be reported to the Sponsor pregnancy information on the appropriate form provided in the regulatory binder. While the investigator is not obligated to actively seek this information in former study subjects, he/she may learn of an SAE through spontaneous reporting.
- Any female subject who becomes pregnant while participating in the study will discontinue study treatment and be withdrawn from the study.

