Serum creatinine $\leq 1.5 \times$ ULN and creatinine clearance (CrCl) of >50 mL/min (using the Cockcroft-Gault formula or 24-hour urine collection)

d. Subject must have coagulation function as follows:

Prothrombin time (PT)/international normalized ratio (INR) and activated partial thromboplastin time (aPTT)/partial thromboplastin time (PTT) $<1.3 \times$ ULN, or within target range if taking prophylactic anticoagulant(s)

9. Female subject is eligible to participate if she meets the following criteria:

a. Is not a woman of childbearing potential (WOCBP), OR

b. Is a WOCBP and using a contraceptive method that is highly effective (ie, with a failure rate of $<1\%$ per year), preferably with low user dependency, during the treatment period and for at least 2 months after the last dose of study treatment and agree not to donate eggs (ie, ova and oocytes) for the purpose of reproduction during this period. The investigator should evaluate the effectiveness of the contraceptive method in relationship to the first dose of study treatment. Hormonal contraception efficacy may potentially be decreased due to interaction with sotorasib; therefore, male condoms must be used in addition to any hormonal-based contraception methods.

10. Male subject is eligible to participate if he agrees to the following during the treatment period and for ≥ 3 months after the last dose of study treatment:

a. Refrains from donating sperm (any donation of sperm should be conducted prior to study start)

b. PLUS, either:

c. Abstain from intercourse as his preferred and usual lifestyle (abstinent on a long-term and persistent basis) and agree to remain abstinent, OR

d. Must agree to use a male condom AND should also be advised of the benefit for a nonpregnant female partner to use a highly effective method of contraception as a condom may break or leak

11. Subject must provide unstained, archived, tumor tissue samples collected preferably within the past 3 years. Subjects who do not have archived tissue available are required to undergo a tumor biopsy. Subjects who neither have archival tumor tissue samples nor can provide fresh pretreatment biopsies may still be eligible to participate in the study with approval from the Sponsor Medical Monitor.

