7.2. Subject Discontinuation/Withdrawal from the Study

Subjects may withdraw from the study at any time at their own request, or they may be withdrawn at any time at the discretion of the investigator for safety, behavioral, compliance, or administrative reasons. These withdrawals are expected to be uncommon.

A subject may be withdrawn from the study for any of the following reasons:

- Subject's withdrawal of consent for participation in the study
- Sponsor's decision to terminate the study
- Subject is lost to follow-up
- Death

Upon permanent discontinuation of study treatment for any reason, including for subjects in the Extended-Use Phase, an end-of-treatment (EOT) visit should be completed within 30 days after the last dose of study treatment or before any new antitumor treatment is started.

Following the EOT visit, subjects will be considered to have completed the study. Survival follow up will be discontinued for subjects currently in LTFU.

If the subject withdraws consent for disclosure of future information, the Sponsor may retain and continue to use any data collected before such a withdrawal of consent.

If a subject withdraws from the study, he/she may request in writing destruction of any samples taken and not tested, and the investigator must document this in the site study records.

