8.3.5. Pregnancy

- Details of all pregnancies in female subjects and female partners of male subjects who become pregnant will be collected after the start of study treatment and will be followed to determine the outcome of the pregnancy.
- If a pregnancy is reported, the investigator should inform the Sponsor within 24 hours of learning of the pregnancy and should follow the procedures outlined in [Appendix 4](#).
- Abnormal pregnancy outcomes (eg, spontaneous abortion, fetal death, stillbirth, congenital anomalies, ectopic pregnancy) are considered SAEs.

- Pregnancy reporting as detailed above will continue during the Extended-Use phase of the study and should be reported to Drug Safety on the SAE report form.

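### Appendix 4 ties pregnancy collection to being in the study, which can end before the protocol's own post-treatment contraception periods do, and Section 8.3.5 does not match it

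*Protocol*

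**What the plan says.** **Collection rule in Appendix 4.** For female subjects, the investigator collects information on anyone "who becomes pregnant while participating in this study". For male subjects, it is a female partner "who becomes pregnant while the male subject is in this study". Once the study is over, the appendix asks only for pregnancy-related SAEs that the investigator considers related to treatment. It adds that investigators need not go looking for this in former subjects. That provision sits under the heading for female subjects.

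**Collection rule in Section 8.3.5.** "Details of all pregnancies in female subjects and female partners of male subjects who become pregnant will be collected after the start of study treatment", with follow-up to outcome. A start is given but no end, and sites are referred to Appendix 4 for procedures. The section continues to apply in the Extended-Use phase.

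**When a subject leaves the study.** Section 7.2, which expressly includes the Extended-Use phase, says that the EOT "visit should be completed within 30 days after the last dose of study treatment", or before new antitumor treatment starts. It then states: "Following the EOT visit, subjects will be considered to have completed the study". The synopsis (Section 1.1.3) repeats this. Against it, Table 1 footnote 3 keeps main-study subjects on study after treatment for survival follow-up, and Section 4.1.2 gives them an LTFU period. Both stop LTFU when the Extended-Use phase begins.

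**Contraception periods in Section 5.1.** Criterion 9b requires contraception in women of childbearing potential "during the treatment period and for at least 2 months after the last dose of study treatment". Criterion 10 sets a minimum of "3 months after the last dose of study treatment" for men.

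**The concern.** The protocol asks subjects to avoid conception for 2 or 3 months after last dose, which implies that a pregnancy arising then is of interest. Yet the appendix that tells sites what to collect closes when study participation closes, and Section 7.2 allows that within 30 days of last dose. A site following both texts literally would have no instruction under Appendix 4 to record, for example, a pregnancy conceived on day 45.

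General safety reporting fills the space only in part. Appendix 4 says that pregnancy itself is neither an AE nor an SAE. Under Section 8.3.1, general AE collection ends 30 days after last dose or at alternative cancer treatment, and only related SAEs are reported afterwards. The last scheduled pregnancy test is at EOT (Table 1 footnote 24). What may be lost is therefore normal outcomes, events judged unrelated, and prospective follow-up of an exposed pregnancy. Section 2.2.2.1 lists embryofetal toxicity among effects reported with more than one inhibitor of the RAS pathway, so this information has some value even if cases are few.

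**Working it through.** The plan has no figure to reproduce here. The check compares the two windows and then asks to whom the difference applies.

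**Inputs**
- Latest EOT: day 30 after last dose (Section 7.2).
- Contraception period: at least 2 months for women, at least 3 months for men (Section 5.1, criteria 9b and 10).
- Days per month: 30.4375, the conversion used in SAP Section 7.2.

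**Formula.** Uncovered days = (months × 30.4375) − day on which the subject leaves the study.

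**If the subject leaves the study at EOT**
- Women: 2 × 30.4375 = 60.9 days. With EOT at day 30, 60.9 − 30 = 30.9, about 31 days.
- Men: 3 × 30.4375 = 91.3 days. With EOT at day 30, 91.3 − 30 = 61.3, about 61 days.
- An earlier EOT widens the gap. The limits, with EOT on the day of last dose, are about 61 and 91 days.

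**To whom this applies**
1. *Subjects who stop in the Extended-Use phase.* They have no LTFU, so participation ends at EOT on any reading. The figures above apply in full under Appendix 4.
2. *Subjects whose LTFU is discontinued when the Extended-Use phase begins.* The leaving day is the later of EOT and the LTFU stop. The figures above are reached if LTFU stops by day 30. The gap shrinks to zero if it stops after about day 61 (women) or day 91 (men).
3. *Other main-study subjects.* If Section 7.2 governs, they are in the same position as group 1. If Section 4.1.2 and Table 1 footnote 3 govern, they are still in the study through LTFU, and the gap is zero while LTFU lasts beyond the contraception period.

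**Appendix 4 against Section 8.3.5.** On day 45 after last dose, for a subject who left at EOT, Section 8.3.5 read alone includes a new pregnancy. Appendix 4 does not, unless a related SAE follows. Both cannot be the collection rule.

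**After the fix.** If collection runs to at least the end of the contraception period regardless of EOT, the uncovered interval is 0 days in every group.

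**The case against.** The strongest reply is that the protocol already covers most of this. Section 8.3.5 is the main-text rule, is broad, and refers to Appendix 4 for procedures, not for a time limit. Main-study subjects remain on study through LTFU; SAP Section 2.2.3, written against protocol version 4.0, has them telephoned every 3 months (±2 weeks) until withdrawal of consent, death or end of study. Related SAEs stay reportable after day 30, and Section 8.3.5 counts abnormal pregnancy outcomes such as spontaneous abortion, stillbirth and congenital anomaly as SAEs. Much of this stands, and it rules out three stronger readings that a reader might infer:

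- *That at least one of two months (women) and two of three (men) is uncovered for everyone.* This holds only where participation ends by day 30. Table 1 footnote 3 and Section 4.1.2 contradict that for main-study subjects.
- *That these pregnancies would go unreported.* Section 8.3.5 can be read to include them, and related SAEs have a route.
- *That Appendix 4 overrides Section 8.3.5.* No text gives either precedence.

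It is also fair to say that Section 5.1 states contraception and gamete-donation requirements, not a defined risk window, and that embryofetal toxicity is listed for the drug class, not as a finding for either study drug.

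The reply does not remove the conflict. Section 7.2 on its face covers all subjects, Extended-Use subjects have no LTFU, and the LTFU contact is described as a survival call (with anticancer treatment added in the SAP), with no mention of pregnancy.

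**Conclusion.** The point holds as a gap in Appendix 4 plus an inconsistency among Appendix 4, Section 8.3.5, Section 7.2 and the LTFU text. For subjects without LTFU, about 31 of 61 post-dose days (women) and 61 of 91 (men) can lie outside Appendix 4 collection when EOT is at day 30. For other main-study subjects the documents do not settle the size, which runs from zero to the same figures or more. This assumes that Appendix 4's reference to being in the study means what Section 7.2 says about completion, and that the contraception periods are taken at their stated minimums.

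The practical weight is low. The SAP plans about 46 subjects and few pregnancies are to be expected. No efficacy or other planned analysis is affected. The case for acting is that the correction costs almost nothing.

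**What to change.** 1. In Appendix 4, replace "who becomes pregnant while participating in this study" and "who becomes pregnant while the male subject is in this study" with a window running from first dose until at least the end of the post-treatment contraception period in Inclusion Criteria 9 and 10, whether or not the EOT visit has occurred.
2. In Section 8.3.5, state that collection applies at least through that period. Do not write 2 and 3 months as end dates: Section 5.1 gives them as minimums, and a fixed end would narrow a rule that is now open.
3. Reconcile Section 7.2 (and the same text in Section 1.1.3) with Section 4.1.2 and Table 1 footnote 3 on when a subject leaves the study.

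The cost is protocol wording and a reminder to subjects to report a pregnancy during the contraception period. No visit or test is added, and no treatment or contraception requirement changes.
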